7.2 Sample Size Estimation

With 2:1 randomization, it is estimated that 51 patients, 34 for the occlusion group and 17 for the standard care group, are needed to have 80% power to detect a hazard ratio for removal of drain of 2.5, on the basis of a log-rank test with a two-sided significance level of 5%. Assuming a 10% dropout rate, the planned number of patients to be enrolled is 57, 38 for the occlusion group and 19 for the standard care group. All randomized subjects are analyzed according to intention-to-treat.

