3.7 Discontinuation

An individual patient's participation is discontinued if the patient decides to withdraw from the study, or the attending surgeon/physician-in-charge advises withdrawal from the trial based on medical reasons. According to intention-to-treat, the data of patients who withdraw from the study after being randomized are included for analysis.

4 Selection and Withdrawal of Subjects

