4.3 Subject Withdrawal

Patients can withdraw from the study after participating in the study. If a patient withdraws before being randomized, the patient is considered as being excluded because of decline to consent. If a patient withdraws after being randomized but before receiving the randomly assigned treatment, the assigned treatment is not given but the patient is included in the analysis according to the randomly assigned group (ITT). The type of treatment is

chosen according to the attending physician and his/her discussion with the patient. After withdrawal, patients are followed according to the follow-up scheme of this trial. The type and timing of the data to be collected for withdrawn subjects are the same as those who remain in the trial. No replacement for withdrawal is attempted.

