6.1 Safety Parameters

Safety end points:

- Fever or pain that develops within 48 hours after the allocated treatment, or any adverse events judged to be related to the treatment.
 - Fever/infection: body temperature $\geq 38.5^{\circ}\text{C}$, leukocytosis (WBC count $>12,000$ /uL) or leukopenia (WBC count $<4,000$ /uL)
 - Pain: new-onset or worsening of pre-existing pain (≥ 1 point increase in VAS).

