7.1 Statistical Methods

Descriptive statistics will be computed for all variables and presented. Continuous variables will be summarized by the number of patients, mean and standard deviation. Categorical variables will be summarized by frequency counts and percentages for each category.

The primary efficacy end point will be compared between the two trial groups using a Log-rank test on an intention-to-treat basis. Cox proportional hazards model is used to analyze the rate of POPF closure with adjustment for covariates. Secondary efficacy end points and safety end points are analyzed using Chi-square tests, Fisher's exact tests, two sample T-tests, Mann-Whitney U tests, and multivariable linear and logistic regression models, where appropriate. In all analyses, statistical uncertainty will be quantified by means of 95% confidence intervals.

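### No safety population is defined, so patients who withdraw before occlusion stay in the denominator of a procedural 48-hour safety endpoint and dilute the occlusion harm rate

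*Combined protocol and SAP*

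**What the plan says.** Four parts of the combined protocol and SAP bear on this point.

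- **Withdrawal.** Under section 4.3, for a patient who withdraws after randomisation but before treatment, "the assigned treatment is not given but the patient is included in the analysis according to the randomly assigned group (ITT". The treatment then given is "chosen according to the attending physician and his/her discussion with the patient". Follow-up continues on the trial scheme: "The type and timing of the data to be collected for withdrawn subjects are the same as those who remain in the trial". Section 3.7 agrees: "According to intention-to-treat, the data of patients who withdraw from the study after being randomized are included for analysis".
- **Analysis set.** Section 7.2 closes with "All randomized subjects are analyzed according to intention-to-treat". Section 7.1 attaches ITT by name to the primary endpoint only: "The primary efficacy end point will be compared between the two trial groups using a Log-rank test on an intention-to-treat basis".
- **Safety analysis.** Section 7.1 lists tests and names no population: "Secondary efficacy end points and safety end points are analyzed using Chi-square tests, Fisher's exact tests", followed by further tests and regression models. No safety set, as-treated set or grouping by procedure received appears anywhere.
- **Safety endpoint.** Section 6.1 defines it as "Fever or pain that develops within 48 hours after the allocated treatment, or any adverse events judged to be related to the treatment". Section 3.1 gives essentially the same definition. Section 6.2 times the pain scores, vital signs and leukocyte count from the assigned treatment.

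**The concern.** ITT is right for the efficacy endpoints, and nothing here questions it. The safety endpoint is different, because it asks what happens in the two days after a procedure. A patient allocated to occlusion who withdraws first is, by rule, not given it. That patient cannot have an occlusion-related event and has no time at which the 48-hour window opens, yet remains in the occlusion denominator if the ITT rule is followed. Each such patient pulls the occlusion harm rate down.

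The opposite movement is possible but less certain. If a patient who withdraws from standard care is then treated by occlusion, related harms could appear in the standard-care column.

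Both movements shrink the apparent harm of the new procedure. Safety is named beside effectiveness in the trial objective (section 2), and the planned arms are small, so a few patients can shift the rates.

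**Working it through.** **Inputs**

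- Planned enrolment (section 7.2): 51 patients (34 + 17) inflated for 10% dropout. 51/0.9 = 56.7, 34/0.9 = 37.8 and 17/0.9 = 18.9, which round up to the stated 57, 38 and 19. These are the denominators of an as-randomised safety table.
- Harm rate p after occlusion: the only figures in the plan are for pain in the pilot study. Section 1.2 gives 3 patients among 20 (15.0%); section 1.3 gives 3 of 14 (21.4%). The two denominators disagree, so both rates are carried through.
- Switching rates: not in the documents. Let a be the fraction of the occlusion arm that does not receive occlusion, and b the fraction of the standard-care arm that does. The 10% used below is an assumption; the plan's own 10% is a dropout rate, not a switching rate.
- Background event rate q: not in the documents; taken as 0 in the main illustration.

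**Formula**

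Occlusion arm as randomised: (1 − a)p + aq.

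Standard-care arm as randomised: (1 − b)q + bp.

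Difference: (p − q)(1 − a − b). The fraction of the harm difference lost is therefore a + b.

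**Results with q = 0, in percentage points**

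| Assumed switching | p = 15.0% | p = 21.4% | Loss |
|---|---|---|---|
| a = 0, b = 0 | 15.0 | 21.4 | 0% |
| a = 10%, b = 0 | 13.5 | 19.3 | 10% |
| a = 10%, b = 10% | 12.0 | 17.1 | 20% |

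**Whole patients, arms of 38 and 19**

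Each untreated occlusion patient removes 1/38 = 2.6% of the difference. Each standard-care patient who receives occlusion removes 1/19 = 5.3%.

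| Occlusion patients not treated | Standard-care patients given occlusion | Loss |
|---|---|---|
| 2 | 1 | 11% |
| 4 | 2 | 21% |
| 6 | 3 | 32% |
| 8 | 4 | 42% |

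With 4 and 2, 15.0 points becomes 11.8 and 21.4 becomes 16.9.

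**Sensitivity to background events**

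With q = 5%, and untreated patients assumed to have events at that rate, the relative loss is unchanged but the absolute differences are smaller. With 4 and 2 switches, 10.0 points becomes 7.9 at p = 15.0%, and 16.4 becomes 13.0 at p = 21.4%.

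**Single event**

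One occlusion-related harm in a standard-care patient who received occlusion would add 1/19 = 5.3 points to the standard-care rate, if it were tabulated there.

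**The case against.** The strongest reply is that this is a wording gap whose effect may be nil. Its parts fare differently.

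- **ITT is tied by name only to the primary endpoint.** This is true of section 7.1, and the broader sentence in 7.2 sits in the sample-size section. A reader might infer that the plan expressly orders ITT for every safety table; the text is less explicit than that. But 3.7, 4.3 and 7.2 all keep these patients in the analysis, 4.3 and 7.2 by ITT without an exception for safety, and nothing else fills the gap.
- **Crossover to occlusion is not stated.** This stands. Section 4.3 leaves the choice to physician and patient; it neither offers nor excludes occlusion after withdrawal from standard care. The interval between randomisation and treatment is probably short, and the trial is described as double-blinded, which makes withdrawal in order to switch less likely. The dilution in the occlusion arm needs no crossover, only non-receipt.
- **The literal endpoint may exclude these events.** A standard-care patient who receives occlusion has not had the allocated treatment, so fever or pain afterwards may fall outside the 48-hour limb. Likewise, an untreated patient might be treated as not assessable instead of event-free. Both readings are possible. The plan does not choose between them, and that choice should not be left until the data are in.
- **Harms can be traced.** Section 6.3 requires, for each adverse event, any interventions performed and the relationship to trial treatment. A reader might infer from 4.3 that the treatment received goes unrecorded for withdrawn patients; collecting the same data as for other patients does not imply that. Tracing single events does not, however, change the planned group rates.
- **Zero background pain is doubtful.** Both arms have fistulography and drain manipulation, and a one-point VAS rise counts as pain. This affects the absolute figures, not the relative loss.

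**Conclusion.** The point holds for safety only. The plan has a rule for withdrawn patients and no safety population. Followed as written, it dilutes the occlusion harm rate whenever an occlusion patient withdraws before the procedure. Harms being tabulated under standard care is a possibility that section 4.3 leaves open, not something it provides for.

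The size cannot be fixed from the documents. With no background events the loss of the harm difference is 0% without switching, 10% with 10% non-receipt in the occlusion arm alone, and 20% with 10% in each direction. A reader might take the 20% as the expected bias. It is not: it needs 10% of standard-care patients to receive occlusion, and no figure in the plan supports that. The amendment is still worth making, because the direction favours the new procedure, the arms are small, and the correction costs little.

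**What to change.** Keep ITT for all efficacy endpoints. In sections 7.1 and 7.2:

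1. State that the 48-hour safety endpoints and procedure-related adverse events are analysed by the procedure actually received (fistulography with occlusion, or fistulography without), with the 48-hour window starting at that procedure.
2. Show alongside an as-randomised table of all adverse events in all randomised patients. Patients who had neither procedure are then still reported, consistent with section 6.3, which requires adverse events to be documented in every randomised patient.
3. Tabulate by arm the procedure received and its date, so that the number of switches is visible. Confirm that the eCRF holds both items for patients who withdraw under section 4.3.

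The cost is a few sentences, one extra table and, if the items are not already captured, a small eCRF addition. The downside is that the by-procedure safety comparison is not strictly randomised for the few patients concerned; the as-randomised table lets the reader judge how much that matters.

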7.3 Significance

The level of significance is 5%.

7.4 Termination Criteria

The trial is terminated when the number of subjects enrolled reach the planned number of enrollment.

7.5 Accountability Procedure

Medical records and case report forms are reviewed to resolve missing or implausible data.

7.6 Deviation Reporting

Any deviation from the original statistical plan and the justification for such deviation are described in the protocol as an amendment and in the final report.

8 Direct Access to Source Data/Documentation

All investigators will permit monitoring, audits, review of ethical committees and regulatory authorities direct access to source data and documents.

9 Quality Control and Quality Assurance

The principle investigator will have responsibility for training trial site investigators, research nurses, and other research assistances before the initiation of the trial. After initiation, the trial site investigators and research nurses will be responsible for entering all relevant data into the electronic case report forms (CRFs). The CRFs will be constructed to ensure data quality with reliable values. This data quality procedure will make sure that the trial data is processed accurately.

10 Ethical Considerations

This study will be conducted according to Good Clinical Practice. This protocol and any amendments will be submitted to the National Taiwan University Hospital Institutional Review Board (IRB) for formal approval to conduct the study. All subjects for this study will be provided a consent form describing this study and providing sufficient information for subjects to make an informed decision about their participation in this study. This consent form will be submitted with the protocol for review and approval by the IRB. The formal consent of a subject, using the IRB-approved consent form, will be obtained before that subject is submitted to any study procedure. This consent form must be signed by the subject or legally acceptable surrogate, and the investigator-designated research professional obtaining the consent.

11 Data Handling and Record Keeping

All data will be kept according to the regulations (e.g. Personal Data Protection Law, Human biological database management regulations) in Taiwan. Individual patient data will be entered into the electronic database built by Research Electronic Data Capture

(REDCap) and be kept strictly within the research team in National Taiwan University Hospital. The data will be analyzed anonymously. The study data will be maintained for 15 years if requested by the relevant authorities.
